6.5 Investigational Product Accountability and Compliance

6.5.1 Assembly of Investigational Product

The Sponsor will provide the P3P piercing accessory, the P3P tube-shaped body and front plug and the P3P capsules according to local regulations.

The P3P capsule should be inserted in the P3P body no earlier than 2 hours prior to product use and the assembled product should be activated by piercing the capsule immediately before product use.

Responsibility for assembly and activation of the investigational product will be held by the investigational site pharmacist or other adequately trained investigational site collaborator.

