8.7 Investigational Product Malfunction and Misuse

Any occurrence of P3P malfunction or misuse (use not in accordance with its instruction) by a subject will be documented by the Investigator using a Product Issue Log. Information regarding product malfunction or misuse should be actively collected during the study visits.

Furthermore, any malfunction or misuse of P3P that leads to an AE/SAE will follow the same processes as described above.

Confidentiality Statement

Data and information contained in this document are considered to constitute trade secrets and confidential commercial information, and the legal protections provided to such trade secrets and confidential information are hereby claimed under the provisions of applicable law. No part of this document may be publicly disclosed without the written consent of Philip Morris Products S.A.

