In general, all safety data will be listed and tabulated using the approach described in section 12.1.3. Safety variables collected during exposure periods will also be reported by product exposure.

AE data will serve for the primary assessment of safety. Other safety variables monitored in this study include: incidence and frequency of P3P product events including malfunction/misuse; respiratory symptoms (cough assessment VAS and Likert scales); vital signs (systolic and diastolic blood pressure, pulse rate, respiratory rate); spirometry; ECG data; clinical chemistry, hematology, and urine analysis safety panel; physical examination; concomitant medications.

All safety data will be listed and AEs will be summarized by product variant (fixed puffing regimen and *ad libitum* use periods will be combined at the product variant level). Safety measurements assessed both after fixed puffing regimen and *ad libitum* use (vital signs, ECG etc.) will be summarized per fixed puffing/*ad libitum* use regimen and product variant.

Confidentiality Statement

Data and information contained in this document are considered to constitute trade secrets and confidential commercial information, and the legal protections provided to such trade secrets and confidential information are hereby claimed under the provisions of applicable law. No part of this document may be publicly disclosed without the written consent of Philip Morris Products S.A.

The number and percentage of subjects with AEs, SAEs, and product events will be tabulated by system organ class and preferred term. Summaries will also be presented for AEs leading to discontinuation, AEs leading to death, AEs by relatedness to product exposure (with and without laboratory related AEs), AEs by severity, and laboratory AEs. Tabulations will be performed for both the number of subjects experiencing an event and the number of events.

Safety laboratory assessments are performed on Day 2 to Day 5 in the morning prior to product use (Appendix A). Any lab related AEs will be assigned to the product used on the previous day.

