## 4.1 Definitions for Statistical Analysis

The following special terms are used in this SAP:

Baseline	For PK/PD analysis and VAS-craving assessment, baseline is defined as the last assessment prior to time point of start of product use at the fixed puffing regimen ( $T_0 \text{ fix}$ ) for fixed puffing regimen and as the last assessment prior to time point of start of first product use at the ad libitum use period ( $T_0 \text{ ad lib}$ ) for ad libitum use, for each study day of exposure. For all the other endpoints, the baseline is defined as the last available assessment prior to $T_0 \text{ fix}$ on Day 1, except for vital signs, where baseline is defined as the last assessment prior to $T_0 \text{ fix}$ for each study day of exposure.
Safety follow-up	After discharge on Day 5 or after discontinuation, a 7-day safety follow-up will be done
End of Study	The end of the study (EOS) for a subject is defined as either the Discharge at Day 5, or the date of early termination of the subject, plus the 7 days for the Safety Follow-up Period. The end of the whole study corresponds to the individual EOS of the last subject.
Enrollment	On Admission Visit for eligible subjects after all applicable inclusion and exclusion criteria have been satisfactorily assessed and met.
Randomization	Assignment to the respective sequence of product use at Day 2.
Screen failure	Subject who signs the ICF but is not enrolled.

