### 12.6.5.1 Safety Reporting

Safety data will be tabulated on the safety population by exposure period defined as:

- Pre-dose Period: Prior to any Product Use [ICF , first use of P3P 3 test at Day-1[. According to protocol, first use would be P3P 3 product test at Day-1].
- Product Test Period: [First use of P3P 3 test at Day-1, First use of P3P 3 at Day 1[
- P3P 3 Period: [First use of P3P 3 at Day 1, First use of product at Day 2 or time of discharge[
- P3P 1 Period: [First use of P3P 1, First use of the next product variant or time of discharge[
- P3P 2 Period: [First use of P3P 2, First use of the next product variant or time of discharge[
- P3P 4 Period: [First use of P3P 4, First use of the next product variant or time of discharge[
- Safety Follow-Up Period : [from time of discharge, 7 days after discharge].

Safety data will be assigned to the specific safety period where the collection time or start time of the AE is included between beginning and the end of the period.

All AEs occurring from the time of signing of informed consent will be recorded and listed.

Only product emergent AEs will be summarized (the ones occurring during pre-dose period will be listed only). If an AE occurs during the Safety follow up period, then this AE will not be assigned to the last product used but summarized in the Safety Follow-Up Period.

A product emergent AE is defined as an AE that occurs after first P3P product use or that is present prior to first product use and becomes more severe after first product use. All other AEs will not be summarized but provided in listings only.

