#### **12.6.5.3 P3P Product Events and Malfunctions**

All events (product malfunction/misuse) related to the P3P will be listed for each subject, including event description, severity of event, AE relationship, action taken and onset/stop dates/times.

Product events will be listed (Listing 15.3.6.2) and summarized by exposure period and overall:

- Number of product events and the number and percentage of subjects reporting at least one product event (Table 15.2.6.9);
- Number of product events and the number and percentage of subjects categorized by severity of product event (minor, major) (Table 15.2.6.9);
- Number of product events and the number and percentage of subjects categorized by AE relationship (related, not related) (Table 15.2.6.9);

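### Product events are tabulated by periods that open at first use, so a morning unit that fails at assembly or piercing on Days 2 to 4 is counted under the previous day's variant

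*SAP*

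**What the plan says.** SAP 12.6.5.1 defines the exposure periods. They are half-open: each includes the moment of first use and stops short of the next variant's first use. For example: "P3P 1 Period: [First use of P3P 1, First use of the next product variant or time of discharge". Placement is by time: "Safety data will be assigned to the specific safety period where the collection time or start time of the AE is included" between the period's limits. The section makes no exception for product events.

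SAP 12.6.5.3 applies these periods to malfunction and misuse: "Product events will be listed (Listing 15.3.6.2) and summarized by exposure period and overall". The attributes it asks to be listed are the description, severity, AE relationship, action taken, and onset and stop times. No unit or variant identifier is among them.

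Protocol 6.5.1 sets the timing of preparation. On assembly: "The P3P capsule should be inserted in the P3P body no earlier than 2 hours prior to product use". On activation: "the assembled product should be activated by piercing the capsule immediately before product use". Protocol 8.7 sets what is recorded: "Any occurrence of P3P malfunction or misuse (use not in accordance with its instruction) by a subject will be documented by the Investigator".

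The incidence and frequency of product events are named safety endpoints in Protocol 3.2 and SAP 5.2.

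**The concern.** A product event is a property of a physical unit, and the unit belongs to a known variant. The SAP instead allocates it by when it happened relative to first use. On the morning of Day 2, 3 or 4 the unit in hand is the new variant, but until the subject starts using it the previous variant's period is still open. If the capsule is wrongly seated or does not pierce properly, the event goes in the previous day's column.

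On Day 2 this would show a fault in a 2 mg unit against the 1 mg product. On Days 3 and 4 it would move faults among the three 2 mg variants. These tables are where a reader would look for differences in reliability between variants.

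**Working it through.** **Inputs**
- Six sequences with three subjects each (Protocol 6.3; SAP 6.3.1 and 8).
- P3P 3 on Day 1 for everyone; P3P 1, P3P 2 and P3P 4 over Days 2 to 4 by sequence.
- Half-open periods starting at first use (SAP 12.6.5.1).
- One first-unit preparation per subject per morning, before T0 fix (Protocol 6.5.1 and Table 9).
- Assumption: all 18 subjects complete.

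**Step 1: reproduce the plan's figure.** 6 sequences × 3 subjects = 18, as stated. Over four mornings, 18 × 4 = 72 first-unit preparations.

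**Step 2: place each preparation by the clock rule.**
- Day 1: all 18 fall in the Product Test Period. That product is also P3P 3, so the column differs but the variant does not.
- Day 2: all 18 fall in the P3P 3 period, although the unit is a 2 mg variant.
- Day 3: each preparation falls under the Day 2 variant. Each 2 mg variant is used by 6 subjects on Day 2, so 6 fall under each.
- Day 4: each falls under the Day 3 variant, again 6 under each.

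| Variant of unit prepared | Product Test | P3P 3 | P3P 1 | P3P 2 | P3P 4 | Total |
|---|---|---|---|---|---|---|
| P3P 3 (Day 1) | 18 | 0 | 0 | 0 | 0 | 18 |
| P3P 1 | 0 | 6 | 0 | 6 | 6 | 18 |
| P3P 2 | 0 | 6 | 6 | 0 | 6 | 18 |
| P3P 4 | 0 | 6 | 6 | 6 | 0 | 18 |
| Total | 18 | 18 | 12 | 12 | 12 | 72 |

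Preparations placed under another variant: 18 + 12 + 12 + 12 = 54 of 72. Each 2 mg variant loses all 18 of its own first-unit preparations and gains 12 that belong to the other two.

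**Step 3: afternoon units.** Protocol Table 10 has the same variant used in the afternoon as in the morning. Preparation for ad libitum use therefore follows that day's first use and is placed correctly.

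**Step 4: what one event is worth.** SAP 12.6.5.3 reports the percentage of subjects with at least one product event. If a period's denominator is 18 (an assumption; the SAP does not give it), one misplaced event in a subject with no other event takes 1/18 = 5.6 percentage points from one 2 mg column. It adds a similar amount to another column.

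**Step 5: after the change.** Assigning events by the unit's variant leaves 0 of 72 preparations under another variant.

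**The case against.** The strongest reply is that few such events may ever be recorded. Site staff assemble and pierce the units (Protocol 6.5.1), and subjects receive them ready for use (6.5.2). Protocol 8.7 can be read as covering what happens in a subject's hands, so a unit that staff reject before dispensing may never become a subject-level event. The functional check that the protocol describes, whether the capsule spins, happens during use, after the period has opened. SAP 12.1 orders listings by variant where applicable, and 12.6.5.3 lists descriptions and times, so single events could be traced. The tables are descriptive, with no hypothesis attached.

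Most of this stands as a limit on size. It does not remove the gap. Protocol 8.7 can equally be read so that only misuse is tied to the subject. Protocol Table 9 has product events collected throughout the morning schedule, and SAP Table 13 provides for a product being replaced. If a pre-use failure is recorded, the summary table puts it under the wrong variant.

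Two stronger readings are tempting, and the documents do not support them.

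- **Vital signs.** A reader might infer that the pre-use readings are mislabelled too. Applied literally, the general sentence would move 54 of 18 × 4 × 3 = 216 planned Day 1 to 4 readings (25%) to another variant. The SAP has specific rules, however. Section 4.1 treats all other non-PK/PD endpoints alike "except for vital signs, where baseline is defined as the last assessment prior to" T0 fix on each study day. Section 12.6.5.5.3 reports by variant and time point, and Table 16 names the pre-puffing reading as a time point. The pre-use reading is therefore that day's baseline. What is missing is only a statement that these rules take precedence.
- **Laboratory AEs.** Protocol 12.6.3 states: "Any lab related AEs will be assigned to the product used on the previous day". The SAP repeats the previous-day link for laboratory values (12.6.5.4) but not for AEs. A reader might infer that laboratory AEs shift to the next variant. They do so only if onset is dated after the next first use, and no text says that it is. When onset is the pre-use sampling time, the two rules agree.

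**Conclusion.** The point holds for product events in units prepared before T0 fix on Days 2 to 4. On those mornings the stated rule attributes a named safety endpoint to the wrong variant. It bears on 54 preparation occasions with 18 completers. Those are opportunities for misplacement, not events: the documents give no failure rate, so the number of misplaced events could be nil.

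The conclusion assumes that the periods are applied as written, that an event's onset is the time of the failure, and that failures at preparation are logged. Day 1 is not a wrong-variant problem, and afternoon preparation is unaffected. No PK result, sample size or error rate is touched. This should be corrected because the fault is plain and the remedy almost free; it does not threaten the trial's conclusions.

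**What to change.** In SAP 12.6.5.3, state that each product event is assigned to the variant of the unit being assembled, pierced or used, identified from the dispensing log (Protocol 6.5.2) and the Product Issue Log (Protocol 8.7), whatever the clock time. The Day 1 unit then counts under P3P 3, not the product test. Say also whether failures found by staff before dispensing are counted.

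As consistency wording only, add to SAP 12.6.5.1 that vital signs taken before fixed puffing are the baseline of that day's variant, as section 4.1 already defines. Add that laboratory AEs from the scheduled morning samples follow the protocol's previous-day rule. Keep the clock rule for other AEs.

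The cost is a short paragraph and a small change to the derivation of the product-event tables. No new data are needed, provided the logs identify the variant.

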### 12.6.5.2 Adverse Events

All AE will be listed (Listing 15.3.6.1.1) and summarized by exposure period and overall:

- The number of events and the number and percentage of subjects reporting at least one AE (Table 15.2.6.1);

#### Confidentiality Statement

Data and information contained in this document are considered to constitute trade secrets and confidential commercial information, and the legal protections provided to such trade secrets and confidential information are hereby claimed under the provisions of applicable law. No part of this document may be publicly disclosed without the written consent of Philip Morris Products S.A.

- The number of serious/non serious events and the number and percentage of subjects reporting at least one serious/non serious AE (Table 15.2.6.1);
- If applicable, the number of events and the number and percentage of subjects reporting at least one SAE classified by reason for seriousness (Table 15.2.6.1);
- The number of events and the number and percentage of subjects reporting at least one AE broken down by product relatedness (related, not related) (Table 15.2.6.1);
- The number of events and the number and percentage of subjects reporting at least one AE broken down by study procedure relatedness (related, not related) (Table 15.2.6.1);
- The number of events and the number and percentage of subjects reporting at least one AE broken down by expectedness (expected, not expected) (Table 15.2.6.1);
- The number of events and the number and percentage of subjects reporting at least one AE broken down by severity, including a subject once with worst severity (Table 15.2.6.1);
- The number of events and the number and percentage of subjects reporting at least one AE broken down by action taken related to the product (combining the following items: product use interrupted, product use reduced, product use stopped) and other action taken (Table 15.2.6.1);
- The number of events and the number and percentage of subjects reporting at least one AE leading to product discontinuation (Table 15.2.6.1);
- The number of events and the number and percentage of subjects reporting at least one AE leading to study discontinuation (Table 15.2.6.1);
- The number of events and the number and percentage of subjects reporting at least one SAE leading to death (Table 15.2.6.1).

Additional summary tables of AEs will be presented with a breakdown of the number of events, as well as the number and percentage of subjects reporting each AE, categorized by SOC and PT coded according to the MedDRA dictionary (version 20.1):

- The number of events and the number and percentage of subjects reporting at least one AE (Table 15.2.6.2);
- The number of frequent events (i.e. the events with an incidence - calculated as number of subjects reporting the event divided the number of subject included in the safety population - greater than 5%) and the number and percentage of subjects reporting at least one frequent AE (Table 15.2.6.2.1);
- The number of events and the number and percentage of subjects with at least one AE related to study product (Table 15.2.6.3);
- The number of events and the number and percentage of subjects with at least one AE related to study procedures (Table 15.2.6.4);
- The number of events and the number and percentage of subjects with at least one expected AE (Table 15.2.6.5);
- The number of events and the number and percentage of subjects with at least one AE by severity (mild, moderate, severe) (Table 15.2.6.6);

#### Confidentiality Statement

- The number of events and the number and percentage of subjects with at least one AE leading to product discontinuation (Table 15.2.6.7);
- The number of events and the number and percentage of subjects with at least one AE leading to study discontinuation (Table 15.2.6.8);

If a subject has more than one occurrence of the same AE, the subject will be counted only once within a PT for each sequence, with the worst occurrence based on the presentation (e.g., for presentation by severity = most severe, for presentation by relationship = most related). Missing information on the intensity of AE will be counted as severe.

#### **12.6.5.2.1 Serious Adverse Events (Including Deaths)**

All SAE will be listed in a separate listing (Listing 15.3.6.1.2) and summarized as described in section 12.6.5.2 (Table 15.2.6.1).

#### **12.6.5.2.2 Adverse Events Leading to Study Discontinuation**

AEs leading to study discontinuation will be listed in a separate listing (Listing 15.3.6.1.3) and summarized as described in section 12.6.5.2 (Table 15.2.6.1).

#### **12.6.5.3 P3P Product Events and Malfunctions**

All events (product malfunction/misuse) related to the P3P will be listed for each subject, including event description, severity of event, AE relationship, action taken and onset/stop dates/times.

Product events will be listed (Listing 15.3.6.2) and summarized by exposure period and overall:

- Number of product events and the number and percentage of subjects reporting at least one product event (Table 15.2.6.9);
- Number of product events and the number and percentage of subjects categorized by severity of product event (minor, major) (Table 15.2.6.9);
- Number of product events and the number and percentage of subjects categorized by AE relationship (related, not related) (Table 15.2.6.9);

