6 INVESTIGATIONAL PRODUCTS

6.1 Description of Investigational Products

6.1.1 Investigational Products

P3P will be provided by the Sponsor and its distribution will be controlled by a qualified and appropriately trained designee.

P3P generates an inhalable aerosol from nicotine powder when air is drawn through it. P3P is a single use product that has a body in the form of a tube, similar to a cigarette, and contains a capsule. The capsule is pierced (activated) using a P3P piercing accessory before use. The P3P capsule contains nicotine powder composed of either solely nicotine salt or nicotine salt blended with mentholated flavor powder in a 4:1 ratio. The nicotine powder is generated by spray-drying nicotine, [REDACTED] and [REDACTED]. The nicotine powder has a median particle size of $1.8 \pm 0.2 \mu\text{m}$ or $2.25 \pm 0.2 \mu\text{m}$ allowing deep lung deposition whereas the flavor particles have a particle size $> 50 \mu\text{m}$ and deposit in the oropharyngeal cavity. A single P3P product contains 1 or 2 mg of nicotine, depending on the P3P variant.

The following P3P variants will be tested in this study and differ in nicotine powder particle size, nicotine concentration, and in the absence or presence of a flavoring system:

Table 1 P3P variants tested in this study

P3P variant	Nicotine content	Nicotine powder particle size	Total amount of nicotine/ product	Contains flavor particles
P3P 1	5%	$2.25 \pm 0.2 \mu\text{m}$	2 mg	no
P3P 2	5%	$2.25 \pm 0.2 \mu\text{m}$	2 mg	yes
P3P 3	2.5%	$2.25 \pm 0.2 \mu\text{m}$	1 mg	yes
P3P 4	5%	$1.8 \pm 0.2 \mu\text{m}$	2 mg	yes

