6.2.2 Investigational Period (Day 1 to Day 5)

Each subject will use P3P 3 on Day 1. In the morning of Day 2, subjects will be randomized to one of six sequences in order to cross-over to the use of P3P 1, P3P 2 and P3P 4 on Days 2, 3 and 4 (section 6.3).

On each assessment day (Day 1 to Day 4), following at least 10 hours of abstinence from any tobacco and nicotine containing products, subjects will use the assigned product for the given visit with two product use regimen as described in Figure 2:

- using a fixed puffing regimen comprising of 12 puffs in total at a rate of one inhalation every 30 seconds (\pm 5 seconds) in the morning.
- using *ad libitum* use period for 60 minutes (\pm 5 minutes) in the afternoon.

A puffing topography device will be attached to each P3P. There will be one recording of HPT parameters per product. Each P3P product will be weighed before and after product use to estimate the amount of nicotine delivered in the aerosol. During the *ad libitum* use period, the subjects can use the product according to their puffing behavior, without restrictions in the number of puffs, interpuff interval duration or number of products used. The number of P3P products used during the *ad libitum* use period will be recorded. The start and stop time of each product used during each puffing regimen will be recorded as well as the total number of puffs taken at the fixed puffing regimen.

The start of product use for fixed puffing and for the *ad libitum* use period will be defined as T_0 fix and T_0 ad lib, respectively. There will be a washout period of 10 hours between T_0 fix and T_0 ad lib.

There will be no product use on the Discharge day (Day 5).

Except for the assigned products, subjects will not be allowed to use any nicotine-containing products through Discharge or early termination.

Subjects will be continuously supervised by the investigational site staff during P3P use.

Confidentiality Statement

Data and information contained in this document are considered to constitute trade secrets and confidential commercial information, and the legal protections provided to such trade secrets and confidential information are hereby claimed under the provisions of applicable law. No part of this document may be publicly disclosed without the written consent of Philip Morris Products S.A.

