## **12.5 Extent of Exposure (Product Consumption)**

Details of the product test and product use with all products will be listed. The number and percentage of subjects using 1, 2 or 3 P3P 3 products at product test, the number of puffs and duration of product use during the fixed puffing regimen and the number of products used and the total duration of product use during the ab libitum use (calculated as the sum of the durations of each product use) will be summarized per product variant for PK population and Safety (Listing 15.3.2.1, Tables 15.2.2.1 and 15.2.2.2).

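### The product-event table gives event counts and subject percentages by variant period with no denominator of units, although ad libitum use is unrestricted

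*SAP*

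**What the plan says.** SAP 12.6.5.3 lists every product malfunction or misuse and has these events "summarized by exposure period and overall". The measures in Table 15.2.6.9 are "Number of product events and the number and percentage of subjects reporting at least one product event", then the same pair split by severity of the product event and by its relationship to an AE. Protocol 12.6.3 plans the same two kinds of measure: subjects with an event, and events.

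The exposure periods in SAP 12.6.5.1 are variant periods. One example is "P3P 1 Period: [First use of P3P 1, First use of the next product variant or time of discharge". There are parallel periods for P3P 2, 3 and 4, plus pre-dose, product test and safety follow-up. The table therefore sets the four variants side by side.

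On use, Protocol 6.1.1 states that "P3P is a single use product". Protocol 6.2.2 allows ad libitum use "without restrictions in the number of puffs, interpuff interval duration or number of products used", and has the number of products used ad libitum recorded. SAP 12.5 summarises, per variant, "the number of products used and the total duration of product use" for ad libitum use (Tables 15.2.2.1 and 15.2.2.2). For the fixed regimen it summarises puffs and duration, not units. Neither document plans product events per product used or dispensed.

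**The concern.** Each unit is opened, pierced, used once and returned, so the unit is what can malfunction. The number of units at risk in a variant period is partly the subject's own choice. A count of events rises in proportion to units used. The percentage of subjects with at least one event also rises with units used, only slightly more slowly. Two variants that fail equally often per unit will therefore show different figures in Table 15.2.6.9 if one is used more. A variant that fails less often per unit can even show the larger figures.

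What is at stake is how a descriptive safety table is read. Incidence and frequency of product events are listed endpoints under the secondary objective of monitoring safety and tolerability, and the table's columns are the variants. Someone deciding which variant to develop further will look across those columns, and nothing in that table shows how many units lie behind each one.

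**Working it through.** **The plan's own figure.** The documents give no expected number of product events and no expected consumption. The one relevant figure is the number randomized: 6 sequences × 3 subjects = 18 (Protocol 12.2, SAP 8), which reproduces.

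**Inputs**
- Subjects per variant: 18, from the documents.
- Fixed regimen: one unit per subject (assumption).
- Ad libitum units per subject: 3 for one variant and 6 for another (assumption). Units in the variant period are then m = 1 + 3 = 4 and m = 1 + 6 = 7.
- Event probability per unit p: 2%, with a range of 1% to 5% (assumption). Units are taken as independent.

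**Formulas**
- Expected events = 18 × m × p
- Proportion of subjects with at least one event = 1 − (1 − p)^m

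**Same reliability, different use**

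| p | Expected events, m = 4 | Expected events, m = 7 | Ratio | Subjects, m = 4 | Subjects, m = 7 | Ratio |
|---|---|---|---|---|---|---|
| 1% | 0.72 | 1.26 | 1.75 | 3.9% | 6.8% | 1.72 |
| 2% | 1.44 | 2.52 | 1.75 | 7.8% | 13.2% | 1.70 |
| 5% | 3.60 | 6.30 | 1.75 | 18.5% | 30.2% | 1.63 |

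For p = 2%: 18 × 4 × 0.02 = 1.44 and 18 × 7 × 0.02 = 2.52; 1 − 0.98^4 = 0.078 and 1 − 0.98^7 = 0.132.

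**The order can reverse.** Take a variant with p = 4% and 2 ad libitum units (m = 3), and another with p = 2% and 8 ad libitum units (m = 9).
- First: 18 × 3 × 0.04 = 2.16 events; 1 − 0.96^3 = 11.5% of subjects.
- Second: 18 × 9 × 0.02 = 3.24 events; 1 − 0.98^9 = 16.6% of subjects.

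The variant with half the event probability per unit has the larger figures on both planned measures.

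**With a denominator of units.** At p = 2%, 1.44 events over 18 × 4 = 72 units is 2.0 per 100. For the other variant, 2.52 events over 18 × 7 = 126 units is also 2.0 per 100. The dependence on consumption disappears.

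**Precision.** The chance of seeing no event at all is 0.98^72 = 23% for the lighter-used variant and 0.98^126 = 8% for the heavier-used one. With so few events expected, a rate per unit will be unstable too.

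**The case against.** The strongest reply is that the plan never sets out to compare variants on product events. The contrasts of interest (P3P 2 against 3, 4 and 1) are specified for PK and PD endpoints only. There is no hypothesis, no confidence interval for product events, and SAP 12.1.8 calls the study descriptive. The planned counts and percentages also deliver what the protocol named, incidence and frequency. This stands. A reader might infer that the plan will rank variants on reliability from raw counts, but the documents contain no such step. What remains is a table whose columns are the variants and which lacks its natural denominator.

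Second, much of the information is reported elsewhere. Ad libitum units are summarised per variant, including for the Safety population, and all product use is listed. A careful reader could assemble an approximate rate. That is true, and it limits the harm. The reader would still have to join separate tables, and SAP 12.5 does not summarise units for the fixed regimen.

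Third, the size is assumed. A reader might suppose that the 1 mg variant will be used more to make up for its lower nicotine content. The documents do not say so: Protocol 2.3.3 says only that confinement may increase P3P use in general. Nor does going from 3 to 6 ad libitum units double the exposure. With one fixed-regimen unit in each variant period the ratio is 7/4 = 1.75.

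Fourth, a rate per unit would not isolate product reliability. The endpoint includes misuse by the subject (Protocol 8.7), which need not scale with units. P3P 3 is always used on Day 1, so its rate is confounded with inexperience. Replacement of the product is a recorded action (SAP 7.5, Table 13), so a unit that failed before use may be missing from a count of units used. These points stand. They affect which denominator to use and how the rate is labelled, and they do not argue for leaving the denominator out.

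**Conclusion.** The point holds as a minor gap in description. Table 15.2.6.9 reports product events by variant period without the number of units behind them, and both planned statistics depend on that number. If use differed by 3 ad libitum units per subject as in the example, at 2% per unit, the heavier-used variant would show 1.75 times the expected events and 13.2% against 7.8% of subjects, with no difference per unit. In absolute terms that is about 1.4 against 2.5 expected events, a difference that chance alone could easily produce.

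The figures rest on an assumed event probability, assumed consumption, one unit per fixed regimen and independence between units. If consumption turns out similar across variants, the planned table is not distorted by it. The documents do not support going further and saying that the plan makes a misleading comparison, or that a per-unit rate would be a clean measure of reliability.

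**What to change.** In Table 15.2.6.9, for each exposure period including the product test, add:

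1. The number of products dispensed, taken from the dispensing log (Protocol 6.5.2) and the product-use records, and counting units that failed and were replaced.
2. Product events per 100 products dispensed.
3. The same rate for malfunction and misuse separately, where the Product Issue Log allows them to be distinguished.

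Keep the planned counts and subject percentages. State in SAP 12.6.5.3 that the rate is descriptive only. Add a footnote that P3P 3 is always used first, so its rate also reflects inexperience with the product.

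The cost is a few extra rows in one table and a short definition of the denominator. No new data are needed, because dispensing and ad libitum use are already logged. The downside is that the rate will be imprecise, since few events are likely with 18 randomized subjects.
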